## 9.2.2 Urinalysis

Urinalysis is assessed, using dipsticks, at the same visits as biochemistry and hematology.

Urinalysis results will be listed only.

### **9.2.3 Pregnancy Test and Urine THC Screen**

Serum pregnancy test results and urine THC screen results will be summarized by treatment group and visit.

### **9.2.4 MECP2**

Results from the *MECP2* genetic mutation assessment at screening will be listed, along with demographic data in one listing. The listing will indicate whether the *MECP2* genetic mutation was known at screening or whether it was obtained from laboratory results.

## **9.3 Vital Signs, Other Physical Findings and Other Safety Data**

### **9.3.1 Vital Signs**

Vital signs (systolic blood pressure, diastolic blood pressure and pulse rate) are measured at Visit 1 (screening), Visit 2 (Day 1), Visit 5, Visit 6, Visit 7, Visit 8, Visit 9 (end of treatment) and Visit 10 (end of taper).

Summaries will be presented by treatment group for each vital sign parameter at each visit. Change from baseline to each post-baseline visit will also be presented.

A separate table will be produced, by treatment group and visit, presenting the incidence of patients with vital signs indicative of a medical condition at Visit 1 and indicative of an AE after Visit 1.

Based on the criteria presented in [Appendix 3](#), potentially clinically significant changes from baseline in vital signs measurements and other defined flagged values will be identified at each visit. The number of patients with a potentially clinically significant change from baseline will be summarized by parameter, visit and treatment group. The number of patients with at least one post-baseline flagged vital sign parameter value will be summarized by parameter, flagged criteria and treatment group.

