9.2.8 Vital Signs

Vital sign measurements (blood pressure and pulse rate) will be taken in a sitting position at rest for 5 minutes. Blood pressure should be recorded using the same arm throughout the trial, where possible.

9.2.9 12-Lead Electrocardiogram

TriPLICATE ECGs will be performed after 5 minutes rest. TriPLICATE ECGs should be taken as close together as possible. An ECG machine will be provided to all sites and all ECGs will be reviewed by a central reader. The central reader will provide a report within 24 hours of collection of the ECG. Additional alerts will be sent to the site in the case of clinically relevant abnormalities. The central reader will provide measurements and an overall assessment to support the investigator in their final assessment. If needed, the investigator may update clinical relevance based on patient files, medical history and any clinical symptoms. The central reader can be supportive for any discussions on patient outcomes. Any abnormal findings considered to indicate significant medical history or AEs must be recorded appropriately on the eCRF. In addition to the scheduled assessments, additional ECG measurements can be taken at any time during the trial, if clinically indicated.

Study Code: GWND18064

EudraCT Number: 2018-003370-27

Clinical Protocol 4.1, 07Jul2020 (duplicate synopsis removed)

Overall ECG measurements at screening must show no clinically relevant abnormalities and the average of the 3 QTcB measurements must be \leq 450 msec, to confirm patient eligibility.

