#### **3.3 Study Population**

Female or male patients aged 2–18 years (inclusive), who weigh at least 10 kg may enter the trial. Patients must have a clinical diagnosis of RTT (typical or atypical), defined according to RettSearch Consortium criteria. Patients must have a confirmed pathogenic genetic mutation of the *MECP2* gene. Patients can be enrolled if they qualify for inclusion criteria and if they do not meet any exclusion criteria. For complete list of inclusion/exclusion criteria, please consult clinical study protocol.

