## 7.3 Demographics and Other Baseline Characteristics

The following demographic data will be summarized by treatment group and overall for the safety and ITT analysis sets:

- Age (years);
- Age group (2-5 years, 6-12 years and 13-18 years);
- Sex;
- Race;
- Ethnicity
- Country;
- Region (United States, Rest of the World);
- Weight at baseline (kg);
- Height at baseline (cm);
- Body mass index at baseline (kg/m^2);

The following baseline characteristics will be summarized by treatment group and overall for the safety and ITT analysis sets:

- CSS Score;
- CSS stratum;
- Previous use of cannabis.

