where AT is AST or ALT, and treatment emergent is defined as criteria not met at baseline, but met at any time post-baseline. For each of these parameters, a patient with value  $> 8$  ULN will also fall into the  $>3$  and  $>5$  ULN categories.

The above will be summarized overall and for the following subgroups:

- Valproic acid use (as a concomitant medication) (Yes, No).
- Clobazam use (as a concomitant medication) (Yes, No).
- Valproic acid use and Clobazam use (as concomitant medications) (Yes/Yes, Yes/No, No/Yes, No/No).  
(A medication will be considered concomitant if it has a start date on or after the first dose of IMP or if it was started prior to the first dose of IMP and was ongoing.)
- Patients taking 3 or more current AEDs.
- Patients taking 4 or more current AEDs.

All laboratory data will be listed; listings will include limited demographic information about the patient (age, sex, race and weight at baseline). Abnormal laboratory values will be listed separately. A further listing will be created for the laboratory reference ranges and toxicity limits. A listing of liver parameters (ALT, AST, bilirubin and INR) will be produced that includes the baseline result, result at the particular visit, change from baseline, upper limit of normal (ULN) value, ratio of result to baseline and ratio of result to ULN.

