**Table 8 Ranges for Potentially Clinically Significant Changes in Vital Signs**

Vital Sign	Range
Sitting Systolic BP (mmHg)	Change: < -20, > 20
Sitting Diastolic BP (mmHg)	Change: < -10, > 10
Pulse Rate (bpm)	Change: < -10, > 10
Weight (kg)	Percent Change: $\leq -7, \geq 7$

Defined flagged values that will be used to identify low or high vital signs parameters (See [Section 9.3.1](#)) are presented in [Table 9](#).

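### The vital-sign flag table uses one set of limits for ages 2 to 18 and counts flags already present before dosing, so a difference between arms is diluted and depends on age mix

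*SAP*

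**What the plan says.** SAP 9.3.1 identifies flagged vital-sign values at each visit and then reduces them to one count per limit: "The number of patients with at least one post-baseline flagged vital sign parameter value will be summarized by parameter, flagged criteria and treatment group". No condition is set on the patient's status before dosing.

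The limits are in SAP Appendix 3, Table 9. For the signs that are collected there are eight: systolic pressure below 90, above 140 and above 160 mmHg; diastolic below 50, above 90 and above 100 mmHg; pulse below 60 and above 100 bpm. None is banded by age, and SAP 3.3 admits patients from 2 to 18 years. SAP 7.3 defines age groups 2–5, 6–12 and 13–18, but only for the demographic summary.

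For liver enzymes, SAP 9.2.1 does set a baseline condition: "treatment emergent is defined as criteria not met at baseline, but met at any time post-baseline". Haematology, biochemistry and Tanner stage also get shift tables from baseline. Vital signs get neither.

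Table 9 also lists temperature and respiratory rate. Protocol 9.2.8 names what is measured: "Vital sign measurements (blood pressure and pulse rate) will be taken in a sitting position at rest for 5 minutes". SAP 9.3.1 likewise lists only systolic pressure, diastolic pressure and pulse.

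The same SAP section plans other vital-sign outputs. On continuous values: "Change from baseline to each post-baseline visit will also be presented". On the change criteria of Table 8: "The number of patients with a potentially clinically significant change from baseline will be summarized by parameter, visit and treatment group".

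**The concern.** Vital signs are a stated safety endpoint (SAP 2.2.2). Resting pulse falls and blood pressure rises through childhood, so a single limit means different things at 3 and at 17 years. A young child with a pulse of 110 before dosing and 110 at every later visit enters the table as a flagged case, although nothing has changed.

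Two consequences follow. First, flags present before dosing add the same background to every arm and shrink any true difference. Second, because the background depends on age, an age imbalance between arms can move the count without any drug effect. Randomisation is stratified by CSS severity only (SAP 3.5), and the trial was discontinued (SAP 9.5), so a chance imbalance is possible. With purely descriptive reporting, readers will compare these counts directly, and no model adjusts for age or baseline.

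**Working it through.** The plan states no figure for vital-sign flags, so there is none to reproduce. The working has two parts, both resting on assumed inputs.

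**1. Dilution by flags present before dosing.** Let b be the share of patients who meet the limit at baseline and again afterwards. Among the rest, let the risk of a new flag be q on placebo and e on drug.

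- Planned count on placebo: b + (1 − b)q
- Planned count on drug: b + (1 − b)e
- Difference: (1 − b)(e − q)

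Take q = 10% and e = 30% (assumed), a true difference of 20 points:

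| b (assumed) | Placebo | Drug | Difference shown |
|---|---|---|---|
| 0% | 10% | 30% | 20 points |
| 10% | 19% | 37% | 18 points |
| 30% | 37% | 51% | 14 points |
| 50% | 55% | 65% | 10 points |
| 70% | 73% | 79% | 6 points |
| 90% | 91% | 93% | 2 points |

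Counted only among patients not flagged at baseline, the contrast is 10% against 30% in every row. The signal disappears only as b approaches 100%.

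**2. How far the background depends on age.** This was checked for one limit, pulse above 100 bpm. The inputs are assumptions, not figures from the documents: mean resting pulse 105, 90 and 80 bpm at ages 2–5, 6–12 and 13–18; between-patient SD 11; within-patient SD 10, then 5. The six post-baseline readings (Visits 5 to 10) come from SAP 9.3.1.

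With patient mean μ distributed N(m, 11²) and within-patient SD s:

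- P(at least one of six readings above 100) = 1 − E[Φ((100 − μ)/s)⁶]
- P(above 100 at baseline) = 1 − Φ((100 − m)/√(11² + s²))

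With s = 10:

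| Age group | Above 100 at baseline | Flagged at least once, no drug effect | Flagged at least once, true +10 bpm |
|---|---|---|---|
| 2–5 | 63% | 92% | 99% |
| 6–12 | 25% | 58% | 84% |
| 13–18 | 9% | 28% | 58% |

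With s = 5 the youngest group is flagged 84% of the time with no drug effect, giving the range 84% to 92%. If the assumed mean at ages 2–5 is varied from 100 to 110 bpm at s = 10, the range is 84% to 96%.

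**Age mix.** With s = 10, if one arm has 10 percentage points more of its patients aged 2–5 and 10 points fewer aged 13–18, its expected count rises by 0.10 × (92 − 28) = 6.4 points with no drug effect.

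**What a baseline condition alone would do.** Under the same assumptions (s = 10), about 81% of patients aged 2–5 who are unflagged at baseline would still be flagged later by chance. The baseline condition and the age-appropriate limits are therefore both needed.

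**The case against.** A reader might infer that the table cannot show a drug effect. It can. Under the assumptions above, a +10 bpm effect moves the count from 58% to 84% at ages 6–12 and from 28% to 58% at ages 13–18; only ages 2–5 sit near the ceiling. With equal thirds by age (assumed), the overall count goes from (92 + 58 + 28)/3 = 59% to (99 + 84 + 58)/3 = 80%.

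A reader might also infer that age dominates the whole table. Only one of the eight usable limits has been modelled, and the pulse means and SDs come from outside the documents. Nothing here shows how often the blood-pressure limits or the low-pulse limit would be met.

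A third tempting inference is that the pulse change limits in Table 8 ("Change: < -10, > 10") are swamped by ordinary visit-to-visit variation. The documents give no within-patient variability, and those counts are planned by visit rather than over all visits. That criticism is not made here.

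The strongest counter-argument is that baseline is already handled nearby. SAP 9.3.1 plans change from baseline at every visit, counts of changes beyond the Table 8 limits, and a table of vital signs indicative of a medical condition at Visit 1 or of an adverse event later. ECG heart rate and its change are summarised separately (SAP 9.3.2), all data are listed, and age is tabulated by arm for the safety set (SAP 7.3). Randomisation balances age in expectation. All of this stands and lowers the severity. None of it repairs the table that counts patients crossing absolute limits.

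**Conclusion.** The point holds as a minor one. Three facts need no assumption: the Table 9 limits are the same for all ages from 2 to 18; the count includes patients who met the limit before dosing, unlike the SAP's liver-test rule; and two Table 9 rows concern signs that are not collected.

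The size is conditional. The dilution factor (1 − b) is exact under the stated definition, but b is unknown; for an assumed b of 10% to 70%, a 20-point difference shows as 18 to 6 points. The near-ceiling at ages 2–5 (84% to 92%) applies to one pulse limit under assumed norms. The supportable conclusion is that the table is diluted and sensitive to age mix. The documents do not support calling it uninformative. With a descriptive analysis, a discontinued trial and change-from-baseline outputs already planned, no formal decision depends on this count.

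**What to change.** In SAP 9.3.1 and Appendix 3:

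- Count only treatment-emergent flags: limit not met at baseline, met after baseline, with patients not flagged at baseline as the denominator. The safety baseline of SAP 6.1.2 serves for this. A shift table from baseline to worst post-baseline value would be an acceptable alternative.
- Present the counts by the existing age groups 2–5, 6–12 and 13–18, using age-appropriate limits from a published reference that the sponsor chooses and fixes before unblinding.
- Delete the temperature and respiratory-rate rows from Table 9.
- Keep the fixed-limit table as a secondary display if wanted.

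The cost is SAP wording and a little programming for an age lookup; no new data are needed. The downside is small cells by age group and arm in a discontinued trial.

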### **9.3.2 Electrocardiogram**

An ECG will be performed at Visit 1 (screening), Visit 5, Visit 6, Visit 7, Visit 8 and Visit 9 (end of treatment).

For each visit, ECG parameters are measured 3 times (5 minutes interval). For statistical analysis, the mean of those values will be taken into account.

Summaries will be presented by treatment group for mean heart rate, RR interval, PR interval, QRS duration, QT interval, QTcB and QTcF, at each visit. Change from baseline to each post-baseline visit will also be presented.

A separate table will be produced, by treatment group and visit, presenting the incidence of patients

Based on the criteria presented in [Appendix 3](#), defined flagged values will be identified at each visit. The number of patients with at least one post-baseline flagged ECG parameter value will be summarized by parameter, flagged criteria and treatment group.

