6.2 Exclusion Criteria

The patient may not enter the trial if ANY of the following apply:

- 6.2.1 Patient meets exclusion criteria for RTT diagnosis (traumatic brain injury, neurometabolic disease, or severe infection that causes neurological problems; grossly abnormal psychomotor development in the first 6 months of life).
- 6.2.2 Patient has clinically significant abnormal laboratory values, in the investigator's opinion.
- 6.2.3 Patient experiences more than weekly seizures (based on history over the last 2 months prior to screening) i.e., CSS 'epilepsy/seizure' score of 4 or 5.
- 6.2.4 Patient is taking more than 2 concurrent AEDs.
- 6.2.5 Any history of suicidal behavior or any suicidal ideation in the last month or at screening.
- 6.2.6 Patient has clinically relevant abnormalities in the ECG measured at screening or randomization (including QT interval, corrected by Bazett's correction formula [QTcB] interval > 450 msec, average of 3 measurements).
- 6.2.7 Patient has any concurrent cardiovascular conditions which will, in the investigator's opinion, interfere with the ability to assess the patient's ECGs or put the patient at risk because of participation in the trial.
- 6.2.8 Patient's first or second degree relative has a history of significant ECG abnormalities, in the opinion of the investigator (e.g., premature cardiac arrest, sudden death).
- 6.2.9 Patient has any known or suspected hypersensitivity to cannabinoids or any of the excipients of the IMP (active or placebo), such as sesame oil.
- 6.2.10 Patient has moderately impaired hepatic function at screening, defined as serum ALT or AST $> 3 \times$ ULN **or** total bilirubin [TBL] $> 2 \times$ ULN.

Study Code: GWND18064

EudraCT Number: 2018-003370-27

Clinical Protocol 4.1, 07Jul2020 (duplicate synopsis removed)

6.2.11 Female patient is of childbearing potential, unless willing to ensure that they or their partner use a highly effective method of birth control (e.g., combined [estrogen and progestogen containing], hormonal contraception^a associated with inhibition of ovulation [oral, intravaginal or transdermal], progestogen-only hormonal contraception^b associated with inhibition of ovulation [oral, injectable or implantable]^b, intrauterine devices/hormone-releasing systems^b, bilateral tubal occlusion^b, vasectomized partner^{b,c}, sexual abstinence^d) during the trial and for 3 months thereafter.

6.2.12 Female patient is pregnant (positive pregnancy test) or lactating.

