**Table 10 Defined Flagged Values for ECG Parameters**

ECG Parameter	Flag
QTc (ms)	> 450, > 480, > 500

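### ECG outliers are counted by absolute QTc only, so a large individual rise that stays at or below 450 ms enters no by-arm count

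*SAP*

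**What the plan says.** **Entry.** Protocol exclusion 6.2.6 turns away patients with a QTcB "interval > 450 msec, average of 3 measurements". Protocol 9.2.9 repeats the same 450 ms limit for the screening triplicate: "the average of the 3 QTcB measurements must be" at or under it.

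**Schedule and data used.** SAP 9.3.2: "An ECG will be performed at Visit 1 (screening), Visit 5, Visit 6, Visit 7, Visit 8 and Visit 9 (end of treatment"). That is one scheduled pre-dose ECG and five on treatment. Triplicates are averaged: "For statistical analysis, the mean of those values will be taken into account". The safety baseline (SAP 6.1.2) is the last value before first dose, which for ECG is normally the screening reading.

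**Flags.** Table 10 has a single row, labelled QTc in ms, with limits "> 450, > 480, > 500". SAP 9.3.2 then states: "The number of patients with at least one post-baseline flagged ECG parameter value will be summarized by parameter, flagged criteria and treatment group". Appendix 3 lets a patient count in more than one tier.

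**Change.** SAP 9.3.2 summarises the ECG intervals, including "QTcB and QTcF, at each visit", and also presents change from baseline at each later visit. Change-based outlier limits exist only in Table 8, for systolic and diastolic pressure, pulse rate and weight. SAP 9.3.1 counts the patients who meet them by visit and arm.

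**The concern.** The ECG is a named safety endpoint, and the protocol has three cardiac exclusions (6.2.6 to 6.2.8). In a report with no hypothesis tests, the flag counts are a main categorical ECG result, so what they count matters.

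Two kinds of patient are poorly served. One has a large rise from a low baseline that ends at or below 450 ms, and no count includes that patient. The other has a usual value a little under 450 ms and needs only a small upward fluctuation at one of five visits to be counted. The > 450 row cannot tell the second patient from someone with a real prolongation.

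The missing formula adds some ambiguity. Eligibility uses QTcB and the SAP reports both QTcB and QTcF, but Table 10 says neither.

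**Working it through.** The plan states no flag rate, QTc mean or QTc standard deviation, so there is no figure to reproduce. Part of the check is a reading of the text. The rest is a simulation on assumed inputs.

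**1. What no count captures (no assumptions).** Take a baseline of 380 ms and a highest on-treatment value of 445 ms. The change is 445 − 380 = 65 ms. Because 445 is not above 450, none of the three tiers is met and the patient contributes zero to every ECG flag count.

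**2. How easily one visit crosses 450 ms.** For a patient with a stable true QTc of *t* and visit-to-visit SD *s*, the chance of at least one value above 450 ms in five visits is 1 − Φ((450 − *t*)/*s*)⁵. With *s* = 10 ms (assumed):
- *t* = 420: 0.7%
- *t* = 430: 1 − 0.977⁵ = 10.9%
- *t* = 440: 1 − 0.841⁵ = 57.8%

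**3. Across an enrolled population with no drug effect.** The model is: true QTc ~ N(mean, between-patient SD); screening value = true + visit noise; keep if ≤ 450; then five further values with independent noise. There were 400,000 simulated patients per scenario. All inputs are assumptions, and the visit SD refers to the triplicate mean.

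| Mean / between SD / visit SD (ms) | Any > 450 | Same, no entry limit | > 450 and rise > 30 | Rise > 30 alone | Rise > 60 |
|---|---|---|---|---|---|
| 410 / 15 / 12 | 5.3% | 6.3% | 1.8% | about 14% | about 0.1% |
| 410 / 20 / 12 | 8.4% | 11.4% | 2.6% | about 14% | about 0.1% |
| 420 / 15 / 12 | 13.9% | 17.3% | 4.4% | about 14% | about 0.1% |
| 420 / 20 / 12 | 16.2% | 22.8% | 4.9% | about 14% | about 0.1% |

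Over a wider grid the > 450 rate runs from 0.4% (400/15/8) to 39.3% (430/15/16). At the planned 84 per active arm, the four cases above give 84 × 0.053 ≈ 4 to 84 × 0.162 ≈ 14 patients. The > 480 tier is at most about 0.3% in these four cases.

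**4. With a true 10 ms rise.** In the same four cases the > 450 rate goes to about 16%, 20%, 32% and 33%. For mean 410, SDs 18 and 10, the > 450 row moves from 5.2% to 14.8% (ratio 2.8) and the combined row from 0.9% to 5.9% (ratio about 6.5). The absolute difference is larger in the > 450 row (9.6 against 5.0 percentage points). The combined row is more specific but not more powerful.

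**5. Formula.** QTcB/QTcF = RR^(1/3)/RR^(1/2). At 100 beats per minute, RR = 0.6 s and the ratio is 1.089, so a QTcB of 450 ms is a QTcF of 450/1.089 = 413 ms. A QT of 330 ms at 110 beats per minute gives QTcB 447 and QTcF 404 ms.

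**The case against.** The strongest reply is that individual prolongation is already visible. SAP 4.1 puts the minimum and maximum in every continuous summary, so the change-from-baseline table prints the largest rise per arm and visit. SAP section 6 lists all data, including derived changes. Protocol 9.2.9 adds central reading with alerts to sites. This stands: the information is not lost. But a maximum shows one patient per visit and does not say how many had a large rise, and a listing leaves the count to the reader.

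The trial is also randomized, and Table 2 provides pooled and separate placebo columns, so background flagging is shown rather than hidden. Triplicate averaging reduces noise, and the upper tiers are nearly free of it. All of that stands.

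On the formula, SAP 9.3.2 counts flags by parameter and lists QTcB and QTcF separately, so both may well be intended. The table shells are a separate document, and one sentence in 9.3.2 about a further ECG incidence table breaks off, so some detail may sit elsewhere. What remains is a label to make explicit.

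Finally, the trial was discontinued (SAP 9.5), so the arms may be well below 84 and the listings easy to read. That lowers the value of extra rows without removing it.

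**Conclusion.** A small, real gap. SAP 9.3.2 and Table 10 have no change-based ECG count, although Table 8 shows that the SAP uses such counts elsewhere. That conclusion rests on the text alone. The size of the background in the > 450 row rests entirely on assumed QTc means and SDs.

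Three stronger readings are tempting, and the documents do not support them:
- **That noise alone flags many patients.** The rate runs from under 1% to 39% depending on inputs the documents do not give.
- **That the > 450 row fills mainly through regression after entry at the same limit.** In the four cases the entry limit lowers the no-effect rate (5.3% against 6.3%, up to 16.2% against 22.8%), and only about 2% to 12% of flagged patients have a true value above 450 ms. The main mechanism is repeated measurement near a fixed threshold.
- **That mean change is the only change analysis.** The maximum change is summarised and individual changes are listed.

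Nor does the background hide a drug effect: a true 10 ms rise still roughly doubles or triples the > 450 rate.

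**What to change.** In SAP 9.3.2 and Table 10, add two counts by arm: patients with any post-baseline QTc increase above 60 ms, and patients with a post-baseline QTc above 450 ms that is also more than 30 ms above baseline. A row for a rise above 30 ms alone may be shown, but at about 14% with no effect in the four cases it is no less noise-prone than the > 450 row. Keep the > 450, > 480 and > 500 rows. Label the rows QTcB, to match eligibility, and repeat them for QTcF.

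The 30 and 60 ms limits are proposed here for reporting only. They are in neither document, and the sponsor may set others if they are fixed before unblinding. They carry no implication for patient management.

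Cost: a few extra rows in one descriptive table, from ECGs already scheduled, with no protocol change. The downside is a slightly longer table.
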